11.9.2. Definition of Serious Adverse Event

An SAE is any AE that results in any of the following outcomes:

- Death
- Life-threatening (subject at immediate risk of death)
- Requires inpatient hospitalization or prolongation of existing hospitalization
- Results in congenital anomaly/birth defect
- Results in a persistent or significant disability or incapacity

Important medical events that may not result in death, be life-threatening, or require/prolong hospitalization may be considered an SAE when, based upon appropriate medical judgment, they may jeopardize the subject and may require medical or surgical intervention to prevent one of the outcomes listed in this definition. Unless fatal, SAEs related to AdV infection or AdV disease do not need to be reported as SAEs for the purposes of this study; these events will be captured as part of the endpoints for the study.

11.9.3. Recording Adverse Events

AEs spontaneously reported by the subject, in response to an open question from study personnel and/or revealed by observation will be recorded during the study. For each AE, the investigator will evaluate and report the onset date, resolution date, intensity (severity), causality (relatedness to BCV or other anti-AdV drug, as applicable), action taken (with BCV or other anti-AdV drug as well as other action taken), seriousness, outcome (if applicable), and whether it caused the subject to discontinue BCV or other anti-AdV drug.

All AEs and SAEs should be recorded on the appropriate AE module of the eCRF. The intensity (severity) of all AEs will be graded according to the NIH/NCI CTCAE grading scales. The CTCAE scales provide unique clinical descriptions of severity for each AE based on the following general guideline:

- Grade 1:** Mild; asymptomatic or mild symptoms; clinical or diagnostic observations only; intervention not indicated
- Grade 2:** Moderate; minimal, local or non-invasive intervention indicated; limiting age-appropriate instrumental ADL (see below)
- Grade 3:** Severe or medically significant but not immediately life-threatening; hospitalization or prolongation of hospitalization indicated; disabling; limiting self-care ADLs
- Grade 4:** Life-threatening consequences; urgent intervention indicated
- Grade 5:** Death related to AE

Instrumental ADLs refer to preparing meals, shopping for groceries or clothes, using the telephone, managing money, etc. Self-care ADLs refer to bathing, dressing and undressing, feeding self, using the toilet, taking medications, and not bedridden.

A copy of the full NIH/NCI CTCAE grading tables is provided in the SRM.

Laboratory abnormalities are usually not recorded as AEs or SAEs. However, laboratory abnormalities independent of the underlying medical condition that require medical or surgical intervention or lead to study drug interruption or discontinuation should be recorded as an AE, as well as an SAE, if applicable. In addition, laboratory or other abnormal assessments (e.g., electrocardiogram, X-rays, or vital signs measurements) that are associated with signs and/or symptoms may be recorded as an AE or SAE if they meet the definitions described in Section 11.9.1 or Section 11.9.2, respectively. The AE term should be reported in standard medical terminology whenever possible. If a laboratory abnormality is part of a syndrome, the syndrome or diagnosis should be recorded as the AE, not the laboratory result (e.g., record anemia, not decreased hemoglobin as the AE). For AEs associated with laboratory abnormalities, the event should be graded on the basis of the clinical severity in the context of the underlying condition; this may or may not be in agreement with the grading of the numeric laboratory abnormality, e.g., anemia may be assessed as Grade 1 (mild) though the recorded hemoglobin falls within the range for a Grade 2 (moderate) value.

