8. TREATMENT OF SUBJECTS

8.1. Administration of Standard of Care

Subjects randomized to the SoC arm in this study will be managed according to local or institutional practice guidelines and any relevant product labelling. The decisions regarding SoC, including administration of therapy, dose and regimen of therapy, modification of immunosuppression, and monitoring will be the responsibility of the clinical team according to institutional guidelines, local practices, and applicable treatment guidelines for the management of AdV infection. Investigators will need to consider the clinical status of the subjects and the local availability of treatment options.

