8.3.2.5. Elevations in Serum Aminotransferases

Treatment with BCV must be interrupted for at least 7 days (i.e., at least 6 full days off drug) if any of the following confirmed abnormalities occur:

1. ALT or AST > 8x ULN and \geq 2x baseline value
2. ALT or AST > 5x ULN and \geq 2x baseline value for more than 2 weeks
3. ALT or AST > 3x ULN and \geq 2x baseline value **and** total bilirubin > 2x ULN **or** PT-INR > 1.5x ULN
4. ALT or AST > 3x ULN and \geq 2x baseline value with the appearance of fatigue, nausea, vomiting, right upper quadrant pain or tenderness, fever, rash, and/or eosinophilia (> 5%)
5. Total bilirubin > 3 mg/dL and \geq 2x baseline value

Abnormal laboratory values should be confirmed at the central laboratory as soon as feasible. Both initial and confirmatory values should be central laboratory values, however, if waiting for central laboratory confirmation is not deemed clinically appropriate, a sample can be drawn in parallel for local laboratory analysis, and if necessary, BCV may be interrupted pending further investigation of the laboratory abnormalities.

If confirmed, increases in serum aminotransferases, as described above, should result in immediate interruption of BCV dosing. The investigations to be undertaken should include, but are not limited to: imaging, testing for hepatotropic infections, evaluations for GVHD, review of other concomitant medication, and possibly liver biopsy, as appropriate. Potential lactic acidosis should also be ruled out. For subjects on azoles, interruption of dosing with azoles should be considered if criterion 2 above is the only one met (i.e., there is no bilirubin elevation).

If an alternate reason for the laboratory abnormalities is identified and after the abnormalities decrease by \geq 1 CTCAE grade below the grade that triggered BCV interruption listed above, dosing with BCV may resume, however, BCV should be administered as a consolidated weekly dose (i.e., 4 mg/kg, up to a maximum of 200 mg, QW in the absence of concurrent cyclosporine, or 2.8 mg/kg, up to a maximum of 140 mg, QW for subjects taking concurrent cyclosporine).

Generally, subjects with persistent and significant ALT or AST elevations (> 5x ULN) should not resume administration of BCV unless there is clear evidence of a causal association with a viral disease being treated. In these cases, continued treatment with BCV may be allowed after discussion and agreement with the Chimerix Medical Monitor (or designee).

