12.6.1. Adverse Events

On-study AEs are those events that occur from Day 1 through Week 16. Only on-study AEs are summarized unless otherwise specified.

For the BCV arm, TEAEs are those events that begin on or after the date of the first dose of study drug and on or before 7 days after the date of the last dose of study drug. For the SoC arm, TEAEs are those that begin on or after Day 1 and on or before 7 days after the date of the last dose of anti-AdV therapy (or Week 16 if no anti-AdV therapy was used in SoC arm).

Follow-up AEs are those that begin beyond 7 days after the last dose of study drug through Week 16.

Summaries (number and percent of subjects) of AEs by system organ class and preferred term will be provided as follows:

- TEAEs
- \geq CTCAE Grade 3 TEAEs
- Treatment-emergent SAEs
- Treatment-related AEs
- \geq CTCAE Grade 3 treatment-related AEs
- Treatment-related SAEs
- AEs resulting in permanent BCV or other anti-AdV drug discontinuation
- AEs requiring BCV or other anti-AdV drug interruption
- AEs requiring dose modification or consolidation of BCV or other anti-AdV drug
- On-study AEs
- \geq CTCAE Grade 3 on-study AEs
- On-study SAEs
- Follow-up AEs
- \geq CTCAE Grade 3 follow-up AEs
- Follow-up SAEs
- SAEs starting after Week 16
- AEs beginning after Week 16 and leading to death

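### Section 11.9.3 ties the laboratory-to-AE trigger to study drug, a term used for BCV, so an asymptomatic liver-test rise during BCV dosing is recorded more readily than the same rise in SoC

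*Combined protocol and SAP*

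**What the plan says.** Section 11.9.3 sets the default: "Laboratory abnormalities are usually not recorded as AEs or SAEs". It then excepts "laboratory abnormalities independent of the underlying medical condition that require medical or surgical intervention", and also those that "lead to study drug interruption or discontinuation should be recorded as an AE". A separate sentence allows abnormal results with signs or symptoms to be recorded. The intervention and symptom routes are open to both arms.

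Section 8.3.2.5 supplies the drug-action trigger for BCV. It lists five confirmed hepatic criteria, the first beginning "ALT or AST > 8x ULN and", and says "Treatment with BCV must be interrupted for at least 7 days" when any is met. The protocol sets no counterpart for the comparator. Section 8.1 says: "Subjects randomized to the SoC arm in this study will be managed according to local or institutional practice guidelines".

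Section 9 uses *study drug* for BCV alone. Section 12.6.1 dates treatment-emergent events from study drug in the BCV arm, but speaks of anti-AdV therapy in the SoC arm and allows for subjects who receive none. Section 5.3.3, the opening of Section 11.9.3 and the table list in Section 12.6.1 all use the wider term *BCV or other anti-AdV drug*. The trigger sentence does not.

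**The concern.** The route from laboratory value to adverse event differs by arm. In the BCV arm a protocol rule forces the drug action, and the drug action prompts the AE record. In SoC no protocol rule forces any action, and a subject on no anti-AdV drug has nothing to interrupt. Read literally, a creatinine rise that stops IV CDV does not meet the trigger either, because CDV is not the study drug.

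Comparing safety between arms is part of the primary objective (Section 5.1). The protocol names aminotransferase elevation as a main BCV toxicity and renal injury as the main CDV risk. Section 12.6.1 plans "Summaries (number and percent of subjects) of AEs by system organ class and preferred term" by arm, including all TEAEs and AEs requiring interruption. The DSMB also receives the interruption AEs (Section 4.5.1). Part of any excess of hepatic AEs under BCV could come from the recording rule rather than the drug.

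**Working it through.** The plan gives no figure on this point, so there is nothing to reproduce. The check has two parts.

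**1. The rules side by side**, for a confirmed, asymptomatic rise that meets a Section 8.3.2.5 criterion and is independent of the underlying condition:

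| Route to an AE record | BCV, while dosing | BCV, after stopping | SoC |
|---|---|---|---|
| Protocol-mandated drug interruption | Always fires | Cannot fire | None exists |
| Discretionary stop of an anti-AdV drug | Not needed | Only on a wide reading of *study drug* | Only on a wide reading, and only if such a drug is given |
| Medical or surgical intervention | Open | Open | Open |
| Signs or symptoms | Open | Open | Open |

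The arms differ only in the first column. Smaller rises, and rises after BCV has stopped, are treated alike.

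**2. Illustrative size.** Let

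- r = true incidence of meeting a criterion from Day 1 to Week 16, set equal in both arms;
- s = share of these events independent of the underlying disease, and so recordable;
- f = share of BCV-arm events that occur on drug;
- q = share of recordable events that are recorded when no mandated interruption applies (SoC, and BCV after stopping).

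All four are assumptions. The documents say only that f is below 1: BCV stops at confirmed clearance (Section 8.3.1), and Section 4.3.3.2 reports a median of 12 to 22 days to undetectable viremia in pediatric subjects of the earlier AdV study, against 16 weeks of AE recording here. Planned arm sizes are 94 and 47 (Synopsis).

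- Recorded rate, BCV = r × s × [f + (1 − f) × q]
- Recorded rate, SoC = r × s × q
- Artefact = difference = r × f × s × (1 − q)

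With r = 10%:

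- Low end (f = 0.4, s = 0.5, q = 0.5): BCV 0.10 × 0.5 × (0.4 + 0.6 × 0.5) = 3.5%, or 3.3 of 94. SoC 0.10 × 0.5 × 0.5 = 2.5%, or 1.2 of 47. Artefact 0.10 × 0.4 × 0.5 × 0.5 = 1.0 point.
- High end (f = 0.7, s = 0.8, q = 0): BCV 0.10 × 0.8 × 0.7 = 5.6%, or 5.3 of 94. SoC 0%. Artefact 5.6 points.
- High-end f and s with q = 0.8: 5.6 × 0.2 = 1.1 points. With q = 1: zero.

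The artefact is proportional to r: 0.5 to 2.8 points at r = 5%, and 2.0 to 11.2 points at r = 20%. If the same criteria are applied by program to both arms, equal true incidence gives equal counts: at r = 10%, 9.4 of 94 and 4.7 of 47, both 10%.

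**The case against.** The strongest reply is that laboratory safety does not rest on AE forms. Section 5.3.3 lists creatinine doubling, tripling and quadrupling, renal replacement therapy, CTCAE grade increases and change from baseline in central-laboratory values. Chemistry is drawn at every visit in both arms (Table 5, Section 11.8.1), and the DSMB sees liver and renal parameters directly. Safety inference is generally not planned (Section 12.6). More interruptions under a mandated rule are also inherent in the design. All of this stands, and it limits the harm. It does not remove the point. The Section 8.3.2.5 criteria are not a listed endpoint, Section 12.6.2 does not define on-treatment values for SoC, and nothing tells the reader to prefer the laboratory tables to the AE tables for the between-arm comparison.

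A reader might infer that every BCV subject who meets a criterion becomes an AE. The text does not support that. The trigger is limited to abnormalities independent of the underlying condition. Non-fatal AdV-related events are exempt (Section 11.9.1), and ALT above 5x ULN is itself among the criteria for hepatic AdV disease (Appendix 5). A diagnosis replaces the laboratory value where there is one.

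A reader might also infer bias in the SAE and Grade 3 or higher tables. SAE criteria (Section 11.9.2) are the same in both arms. Section 11.9.3 grades laboratory-associated AEs on clinical severity rather than on the numeric value, so the effect on the Grade 3 or higher tables is uncertain.

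The literal reading about CDV is also open to challenge, because the same section asks for action taken with either drug. That supports harmonising the wording. It would not help SoC subjects who receive no anti-AdV drug, and stopping CDV would remain discretionary.

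**Conclusion.** The asymmetry is real and follows from the text. It is confined to asymptomatic, confirmed hepatic rises during BCV dosing that are independent of the underlying disease, plus a wording gap for laboratory changes that stop CDV. It reaches the all-grade TEAE tables and the tables of AEs requiring interruption or discontinuation. The central-laboratory grade shifts, creatinine multiples and renal replacement endpoints are untouched.

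The illustration gives about 1 to 6 points at r = 10%, resting wholly on assumed r, f, s and q and on equal true incidence in the arms. A reader might take 5 to 10 points as the likely size. That needs f = s = 1, meaning every qualifying BCV event occurs on drug and is recordable, and the documents contradict both. Nor do they show that CDV nephrotoxicity would go unseen, since it has its own laboratory endpoints. This is worth correcting because it bears on a comparison named in the primary objective. It does not affect the primary efficacy analysis.

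**What to change.** 1. In the trigger sentence of Section 11.9.3, replace *study drug* with *BCV or other anti-AdV drug*, matching Sections 5.3.3 and 12.6.1 and the opening of 11.9.3.
2. In Section 12.6, and in the SAP, state that the between-arm hepatic and renal comparison rests on the laboratory criteria of Section 8.3.2.5 and the creatinine-doubling endpoint. Apply them by program to both arms' central-laboratory data from Day 1 to Week 16, whether or not any drug was interrupted. Define confirmation identically in both arms, because Section 8.3.2.5 prompts repeat samples only for BCV. Criterion 4 also depends on symptoms and should be shown separately.
3. Present AEs requiring drug interruption as a description within each arm, not as a comparison.

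Keep the exclusions in Sections 11.9.1 and 11.9.3 in both arms. Do not require every threshold hit to be recorded as an AE, which would conflict with them. No dosing or interruption rule changes. The cost is a few sentences, one programmed flag on data already collected weekly, and possibly a few more AE forms at SoC sites.

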11.9.4. Relationship to BCV or Other Anti-AdV Medication

An investigator who is qualified in medicine must make the determination of relationship to BCV or other anti-AdV medication for each AE. The investigator should decide whether, in his or her medical judgment, there is a reasonable possibility that the event may have been caused by BCV or other anti-AdV medication. If no valid reason exists for suggesting a relationship, then the AE should be classified as “not related.” If there is any valid reason, even if undetermined, for suspecting a possible cause-and-effect relationship between BCV or the other anti-AdV medication and the occurrence of the AE, then the AE should be considered “related.”

The relationship to BCV or other anti-AdV medication should be assessed using clinical judgment and the following definitions:

“Related”: A temporal relationship exists between the AE onset and administration of BCV or other anti-AdV medication that cannot be readily explained by the subject’s clinical state or concomitant therapies. Furthermore, the AE appears with some degree of certainty to be related, based on the known therapeutic and pharmacologic actions or AE profile of BCV or other anti-AdV medication. In case of cessation or reduction of the dose, the AE may abate or resolve and reappear upon re-challenge.

“Not Related”: Evidence exists that the AE has an etiology other than BCV or other anti-AdV medication. For SAEs, an alternative causality must be provided (e.g., pre-existing condition, underlying disease, intercurrent illness, or concomitant medication).

Any medication(s), including those administered in the SoC arm, that are considered to have caused or contributed to a SAE must be recorded as suspect medication(s) on the SAE form. Additional instructions for completing the SAE form are provided in the SRM.

11.9.5. Occurrence of Pregnancy and Reporting

If a subject suspects that she is pregnant, a urine test will be performed at the site. If the urine test is positive, BCV will be interrupted pending the results of a confirmatory blood/serum test. If the pregnancy is confirmed with a positive blood/serum test, then the subject will be

permanently discontinued from BCV, but should remain in the study and complete all remaining study assessments (with the exception of drug dosing and PK assessments), where possible. If the female partner of a male subject becomes pregnant, the investigator will contact the Chimerix Medical Monitor (or designee) to discuss the most appropriate course of action, up to and including withdrawal of BCV.

Should a pregnancy occur, including in the female partner of a male subject, it must be reported and recorded on a pregnancy report form. However, pregnancy is not regarded as an AE for the purposes of this protocol, unless there is a suspicion that the study drug may have interfered with the effectiveness of a contraceptive medication.

The outcome of all pregnancies (i.e., spontaneous miscarriage, elective termination, normal birth or congenital abnormality) in female subjects and female partners of male subjects must be followed up and documented to the extent possible, even if the subject was discontinued from the study, provided appropriate consent is obtained from the pregnant subject or female partner. All reports of congenital abnormalities/birth defects are to be considered SAEs. Spontaneous miscarriages should also be reported and handled as SAEs. Elective abortions without complications will not be regarded as AEs.

Additional details regarding the reporting of pregnancies is provided in the SRM.

11.9.6. Reporting Serious Adverse Events

All SAEs must be recorded from the time of administration of the first dose of BCV (or the date of randomization for subjects randomized to SoC) until completion of the Week 36 assessment. In addition, any SAE that is considered to be related to BCV and discovered by the investigator at any time after the subject has completed the study should also be reported. Study procedure-related SAE that occurs after a study participant has signed the ICF and prior to administration of the first dose of BCV (or randomization) should also be recorded as an SAE for the purposes of this protocol.

All SAEs should be reported to Chimerix Safety (or designee). The investigator should complete and forward the study-specific SAE Report Form to Chimerix Safety (or designee) according to the specific instructions provided in the SRM. **SAEs must be reported within 24 hours of learning of the event**. Additional follow-up information, if required or available, should be detailed on a follow-up SAE Report Form to Chimerix Safety (or designee) within 1 business day of receipt of the information, or as instructed by Chimerix Safety (or designee). Responses to SAE queries should be provided to Chimerix Safety (or designee) within 1 business day of obtaining the information. The additional information, including any responses to SAE queries, and any follow-up SAE Report Forms should be placed with the original SAE information and kept within the appropriate section of the study file. More detailed information on reporting SAEs to Chimerix Safety (or designee) (including contact information) is provided in the SRM.

Chimerix (or its designee) is responsible for notifying the relevant regulatory authority(ies) of certain events. It is the investigator's responsibility to notify the relevant EC of all SAEs that occur at his or her site. Investigators and the DSMB Chair will also be notified of all unexpected, serious, drug-related events (i.e., 7- or 15-day expedited safety reports) that occur during the study. Each site is responsible for notifying its EC of these expedited safety reports, in accordance with applicable site practices.

12. STATISTICS

All summaries and analyses will be presented in tabular or graphical form. Statistical methods will be described in detail in the Statistical Analysis Plan (SAP), which will be initially finalized as soon as possible during study enrollment with subsequent amendments clearly documenting changes to the plan throughout the study. No amendments to the SAP will be made after the database lock for the primary analysis and subsequent changes will be presented as post hoc analyses. All statistical analyses will be conducted using SAS[®] software, unless otherwise specified in the SAP.

12.1. Determination of Sample Size

A total of approximately 141 subjects will be enrolled into this study. Sample size calculations were based on the primary endpoint, i.e., AAUC through Week 16. Assuming the observed standard deviation of 1.03 log₁₀ copies/mL in AAUC at Week 16 from a comparable subset of SoC subjects, the study has > 90% power with the currently planned sample size to demonstrate superiority of BCV vs. SoC, given that the true difference in means is > 0.6 log₁₀ copies/mL (i.e., an effect size of ~ 0.58). In addition, the overall mortality at Week 16 non-inferiority comparison will have > 80% power in the event that the expected mortality for SoC is 20% to 30% and there is a true mortality advantage of 6% to 9% in favor of BCV ([Feghoul 2015](#), [Hiwarkar 2017](#), [Mynarek 2014](#)).

